Patients from group 1 will be scanned at the NYSPI or CBIC MRI Unit pre/post TMS treatments. TMS treatments for this group will be implemented under [name] protocol and WIRB. Patients from group 2, will receive another cycle of standard versus targeted TMS, 5 times a week for 6 weeks (30 treatments), followed by a taper phase of 6 sessions to cover 3 treatments in week 1, 2 treatments in week 2 and 1 treatment in week 3. For these patients, second visit to NYSPI or CBIC will occur after first cycle finishes and right before second cycle begins. Also will receive a second post-TMS scan after second cycle finishes (see Diagram 3). Patients will be classified as responders to TMS with at least 50% decrease in HDRS-24 scores from baseline. Patients will be classified as non-responders to TMS with less than 50% decrease in HDRS-24 scores from baseline.

Screening:

A phone screen will be used for this study (NT TMS Screening Phone call Script attached). Patients will come to the NYSPI to meet with [name] to verify eligibility, and after the patient signs the informed consent form and the HIPAA authorization, will undergo clinical assessments to assure adherence to all inclusion and exclusion criteria. Eligible patients will be enrolled in the study.

[name] will explain to patients that at NYSPI they will only come for the imaging component and that no treatments will be implemented at the NYSPI site.

MRI, MRS and CBF/CBV Scanning:

Subjects will undergo 3 tesla (3T) brain MRI-MRS-CBF/CBV scanning. None of the imaging modalities used in the study will include exogenous contrasts. MRI scans will be performed at the NYSPI or CBIC MRI facility immediately before and after the rTMS treatment. 1H MRS PRESS TE80, ASL, FSPGR, resting state MB EPI (BOLD) will be performed at 3T. [name] will be responsible of Multiband EPI, PRESS and ASL for this study. To identify coordinates in the left DLPFC we will use functional connectivity (FC) seed based analysis centered on left DLPFC ROIs to identify the site (X) with peak anticorrelation with the sgACC.

DLPFC Mapping for targeted TMS (for group 2):

Targets for focal brain stimulation with repetitive TMS will be modified based on the MRI. Methodology as follow:

I. The subgenual region of interest (ROI) was constructed by placing a 5 mm radius sphere at MNI coordinates (6, 16, -10), masked to include only sampled grey matter voxels. These subgenual coordinates were chosen based on prior studies where a reduction in subgenual activity was associated with antidepressant response across a wide range of treatment modalities (Fox et al., 2012). Resting state functional connectivity across 500 healthy right-handed subjects from the Human Connectome Project data release (<http://www.humanconnectome.org/data/>) was used for initial analyses as an independent cohort to

construct an average group-level functional connectivity map. The entire subgenual functional connectivity map generated from this independent cohort was used as a mask to extract the average time course activation from each MDD patient.

II. Use Matlab software to generate spheres of varying radii on T1W anatomical images centered on node coordinates within the left DLPFC to account for varying focality of different potential cortical stimulation sites. This procedure will include the mapping of ROI spheres to the surface of MNI space, extract the time series courses and compute the correlation with the subgenual functional connectivity map to find the ROI with the highest anticorrelation value (X) that could serve as optimized target for focal brain stimulation. Next, we will warp the best ROI (X) into the subject native volume space for neuronavigation of TMS coil.

TMS Treatments (for group 2):

All standard TMS treatments for group 1 will be implemented at any of [name] offices.

Second cycle of TMS treatments for group 2 will be implemented at any of [name] offices.

Subjects of this group will be randomized to either receive standard versus navigated TMS (3:2). Patients will receive a total of 36 TMS treatments, 5 times a week for the first 6 weeks (30 treatments), followed by a taper phase go 6 sessions to cover 3 treatments in week 1, 2 treatments in week 2 and 1 treatment in week 3.

Using the NeuroStar Therapy System, the subject's motor threshold (MT) will be determined and the coil placed over the left DLPFC guided by Brainsight Neuronavigation device, which uses MRI images loaded into the system to navigate the coil over the target within the DLPFC. All patients from group 2 will receive stimulation over the left DLPFC at 120% of the MT at a frequency of 10Hz; for a total of 3,000 pulses per session. A total of 36 treatment sessions will be provided over 9-weeks. **All treatments will be implemented outside the NYSPI.**

The NeuroStar TMS Therapy System is the first TMS device cleared by the U.S. Food and Drug Administration (FDA) to treat patients with Major Depressive Disorder (MDD) who have not benefited from antidepressant treatment. Treatment parameters in this study will follow FDA approval, i.e. stimulation pattern, time course, device and patient population. The "standard" procedure of coil positioning locates the left DLPFC at 5-cm anterior to the "hand motor hotspot" along the curvature of the scalp. Alternate stimulation site within the DLPFC in each patient will be used to personalize treatments based on their rsfMRI, therefore its application is considered off-label. Please find IDE Decision Worksheet in additional documents related to this study (uploads section).

Brainsight for TMS:

Brainsight is what is generally referred to as a neuronavigator (also often called a frameless stereotaxy device). Its main function is analogous to a GPS, but applied to the brain. The device takes as input, the structural MR images of the subject, and using an infrared position sensor and related accessories, maps the location and orientation of a TMS coil held on the subject's head to the images and displays a representation of the coil on the images.

This provides two important functions. First, it displays a live representation of the coil on the images on the computer screen, allowing the operator to accurately use the MR images (and the anatomy shown by the images) to determine the location of the coil on the subject's head. Second, fMRI images may be overlaid

on the structural images. These images may be used to define a location in the brain to be stimulated and the coordinates of this target stored. While holding the coil on the head, Brainsight indicates in which direction to move the coil to quickly and accurately place the coil over the target. Once placed, the system monitors the coil's activity and can automatically record the coil's position and orientation w.r.t. target for quality assurance. In addition to the coil, the subject's head is also being monitored, so head movement is shown allowing immediate adjustment to the coil or head location to ensure consistent stimulation during the entire TMS session.

[name], president of Rogue Research Inc., is a consultant in this research project to support the portions of the project related to the use of the neuronavigation system and has adapted both navigators to work with Neuronetics stimulator. Please find [name] uploaded in additional documents related to this study (uploads section). Rogue Research, Inc. is the company responsible for neuronavigation. [name], President of Rogue Inc, will be available to ensure procedures for neuronavigation are followed accurately. He has already come to Contemporary Care to interface the Neuronavigational device with NeuroStar TMS devices to ensure proper use of neuronavigation to guide TMS coil.

An IDE is not required for the Brainsight Neuronavigation stereotaxic device. Please find attached a letter from [name], who is President of Brainsight Neuronavigation company that manufactures the device.

Criteria for Early Discontinuation:

CGI-Global, HDRS-24 and C-SSRS will be assessed weekly in patients undergoing second course of TMS **at any of [name] offices, not at NYSPI**. A licensed MD assigned to the study will meet with patients weekly and assess clinical worsening, suicidality, and intolerable side effects. If patients show a worsening of their general psychopathological condition with 50% increase in HDRS-24 scores from baseline on 2 consecutive ratings or any occurrence of a CGI-I score of 6 or 7 will trigger a clinical evaluation and then a clinical judgment as to whether the patient should be discontinued. Such evaluations will be documented in the patient's chart at **Contemporary Care**. If patients miss any three consecutive treatment sessions or any five treatment sessions, they will be dropped from the study, and after treatment recommendations they will be returned to routine clinical management under the supervision of [name].

In case patients appear to be at increased risk for suicide, he/she will be dropped from the study and accompanied to the ER for evaluation. Additionally, intolerable side effects or any medical worsening will result in immediate withdrawal from the study. All patients dropped out from the study will be returned to routine clinical management under the supervision of [name].

Review for any incidental findings on MRI:

In adherence to the revised Incidental Findings Policy for neuroimaging done at Columbia as described in the 3/27/15 memo from the CUMC IRB, MRI research scans will be read by credentialed neuroradiologists within 2 weeks. The subject or his or her individual physician will be contacted by letter with information about their MRI research scan.

You can upload charts or diagrams if any

Criteria for Early Discontinuation

Criteria for Early Discontinuation

CGI-Global, HDRS-24 and C-SSRS will be assessed weekly in patients undergoing second course of TMS at **any of [name] offices, not at NYSPI**. A licensed MD assigned to the study will meet with patients weekly and assess clinical worsening, suicidality, and intolerable side effects. If patients show a worsening of their general psychopathological condition with 50% increase in HDRS-24 scores from baseline on 2 consecutive ratings or any occurrence of a CGI-I score of 6 or 7 will trigger a clinical evaluation and then a clinical judgment as to whether the patient should be discontinued. Such evaluations will be documented in the patient's chart at **Contemporary Care**. If patients miss any three consecutive treatment sessions or any five treatment sessions, they will be dropped from the study, and after treatment recommendations they will be returned to routine clinical management under the supervision of [name] or their referring psychiatrist.

In case patients appear to be at increased risk for suicide, he/she will be dropped from the study and accompanied to the ER for evaluation. Additionally, intolerable side effects or any medical worsening will result in immediate withdrawal from the study. All patients dropped out from the study will be returned to routine clinical management under the supervision of [name] or their referring psychiatrist.

Blood and other Biological Samples

Please create or insert a table describing the proposed collection of blood or other biological specimens
Not applied.

Assessment Instruments

Create a table or give a brief description of the instruments that will be used for assessment

Depressed Patients:

Assessments, including SCID and HRSD will be performed as part of the referring protocol, as listed below.

No independent assessments will be performed as part of the present study.

[name], WIRB protocol #20141643 entitled: "Cognitive Changes During Treatment with TMS for Major Depression", see attachment.

Clinical Assessments at the NYSPI site will include:

1. Interview for DSM-IV-TR Disorders (SCID-IV-TR). SCID, DSM-IV-TR
2. HRSD28-MADRS Interview

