The present study will test this hypothesis on a group of patients with MDD non-responders to standard TMS by conducting pre-treatment functional connectivity to enable targeting of rTMS based upon individualized connectivity maps. These locations will then be used at the NYSPI site and also given to the treating physician ([name]) to optimize target for focal brain stimulation and efficacy across individuals. Of note, patients from group 1 will be scanned at the NYSPI site but will not receive treatment here, whereas group 2 will both be scanned and receive treatment.

Our preliminary data in Fig. 1 shows results acquired from a subset of patients with MDD that reveals an increase in anti-correlation between left-DLPFC and sgACC consecutive to convulsive therapy. These results suggest that ability to deliver TMS pulse to special targets identified on functional connectivity maps (e.g. DLPFC) have the potential to positively confirm their involvement in MDD. Increase in anticorrelation of rsFC signal of these regions after TMS would amount to such evidence. This is exactly what we observed in convulsive therapy as is shown in Fig 1 in which green-blue-purple spectrum on the sgACC rsFC maps are the surface vertexes within BA46 with highest anticorrelation BOLD signal with sgACC. We seek to replicate this effect with targeted TMS in non-responders to standard TMS. Such strategy has the potential to optimize therapeutic efficacy of TMS (see Fig. 1, attached).

Our justification for committing the non-responders to a second cycle of TMS is as following:

- 1) The second cycle will use an entirely different type of TMS, i.e. neuronavigated TMS based on the functional connectivity maps obtained from patients' brain which offers, hereto-forth, the best guide for the efficacy of TMS as shown in Fig. 1.

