- 2) Since the patients for the second cycle are randomized to receive either neuronavigated or standard TMS, we can justify a second cycle of standard TMS by statistics from [name] clinics which are in agreement with application guidelines for the use of TMS (Rossi et al., 2009). As for [name] past experience is concerned, of the 139 patients that received 9 weeks of TMS, 60 responded at the 4 week point and 89 responded at the 8 week point. Of the 79 that did not respond at the 4 week measurement, 42 (more than 50%) responded at the week 8 point. Response is defined here as a 50% or greater reduction in starting Ham D score. As such, while the advantage of the second round of TMS is clear for the patients who receive neuronavigated TMS, even for the patients who receive the second round of standard TMS the above facts demonstrate the advantages of prolonged (4-8 week) treatment by TMS in the form of a 50% favorable outcome in that group of patients.

In addition to resting state functional connectivity, we will also assess glutamate (Glu) concentrations and resting-state cerebral blood flow/volume (rsCBF/rsCBV) in DLPFC and cortical midline structures (CMS) using Magnetic Resonance Spectroscopy (MRS) and Arterial Spin Labelling (ASL), respectively. CMS refer to brain structures situated near the medial wall of the brain and is mainly comprised of the ventral medial prefrontal cortex, dorsal medial prefrontal cortex, anterior cingulate cortex (the supragenual part in particular) and posterior cingulate cortex. Regional increases in Glu release increase the metabolic rate of post-synaptic neurons (28), and surrounding astrocytes (29), leading to regional BOLD signal increases (30). Glu concentrations may therefore be linked to overall functional connectivity patterns (31-34). In particular, Glu levels in left DLPFC in MDD provide an index of local metabolic activity, and abnormalities can be reversed in a dose-dependent manner by rTMS (35). These effects are present not only close to the stimulation site (left DLPFC), but also in remote (right DLPFC, left cingulate cortex) brain regions.

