11. Willingness to undergo randomization to either treatment arm.
12. History of NON-response to rTMS in THIS depressive episode. Assessment of history from patient and/or Clinical Psychiatric History from [name] office

Create or insert table to describe the exclusion criteria and methods to ascertain them

1. Investigators, and their immediate families (defined as a spouse, parent, child or sibling, whether by birth or legal adoption). Self Report
2. Individuals diagnosed by the investigators with the following conditions: Bipolar Disorder (lifetime), any Psychotic Disorder (lifetime), history of substance abuse or dependence within the past year (except nicotine and caffeine). Physician Evaluation SCID, DSM-IV-TR
3. Behavior, which in the judgment of the investigator may hinder the patient in completing the procedures required by the study protocol. Physician Evaluation Private Psychiatrist Reports
4. Individuals with a clinically defined neurological disorder including, but not limited to: tics, space occupying brain lesion; any history of seizures except those therapeutically induced by ECT; history of cerebrovascular accident; history of fainting; transient ischemic attack within two years; cerebral aneurysm, Dementia; Parkinson's Disease; Huntington chorea; Multiple Sclerosis. Physician Evaluation Medical Records
5. Increased risk of seizure for any reason, including prior diagnosis of increased intracranial pressure (such as after large infarctions or trauma), or history of significant head trauma with loss of consciousness for ≥ 5 minutes. Patients Reports
6. Use of any investigational drug within 12 weeks of the randomization visit. Patients Reports
7. Significant acute suicide risk, defined as follow: suicide attempt within the previous 6 months that required medical treatment; or ≥ 2 suicide attempts in the past 12 months; or in the investigator's opinion, has significant risk for suicide based on the current state or recent history. Physician Evaluation
8. Cardiac pacemakers, implanted medication pumps, intracardiac lines, or acute, unstable cardiac disease. Physician Evaluation
9. Intracranial implants (e.g. aneurysms clips, shunts, stimulators, cochlear implants, or electrodes) or any other metal object within or near the head, excluding the mouth, that cannot be safely removed. Physician Evaluation MRI Screening Form

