At NYSPI or at CBIC (Citigroup Biomedical Imaging Center at Weill Cornell Medical College) MRI facility all patients will come to have a brief conversation with [name] to verify eligibility to participate in this study, and to complete fMRI scans. **Clinical assessments pre/post TMS treatments will be implemented at Contemporary Care or NYSPI.** Patients will complete some assessments using StudyTrax.

Group 1 are patients coming from [name] offices who will be scanned at the NYSPI or CBIC MRI Unit pre/post TMS treatments. TMS treatments for this group will be implemented under [name] protocol and WIRB. Group 2 are patients coming from [name] offices who will come to the NYSPI or CBIC site to be scanned at the NYSPI or CBIC MRI Unit pre/post TMS treatments. **A second course of TMS will be implemented at any of [name] offices (only). For both, Group 1 and Group 2, we will be doing the scanning only (at NYSPI or CBIC)** (Table 1. Timing of all Study Procedures attached). **No treatments will be implemented at NYSPI.**

Overview of Study Design:

Patients from [name] offices will be divided in 2 groups. Group 1 (N=30) will be depressed patients undergoing standard TMS for the first time. Group 2 (N=30) constitutes those who have previously demonstrated that they do not respond to standard TMS. MDD patients prescribed to receive standard TMS for the first time (group 1) will have resting-state FMRI in order to see if we can predict their responsiveness based on the functional connectivity maps. Non-responders to standard TMS approaches (Group 2) will be randomized (3:2) to either receive targeted (N=20) or standard (N=10) repetitive TMS (rTMS) treatments. A connectivity-based targeting strategy will be used on patients undergoing targeted

rTMS to optimize target for focal brain stimulation. Response is defined as a 50% or greater reduction in starting HDRS score. Raters and patients in group 2 will be kept blinded to the treatment assignment. All patients referred from the ongoing treatment study will be assessed by 3 tesla brain MRI, MRS and CBF/CBV procedures at baseline and immediately following the final treatment. **At NYSPI we will only do the imaging component. All treatments will be implemented at any of [name] offices.**

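### The 50% response figure used to justify a second cycle of standard TMS is a late-response rate within one course, not a re-treatment rate; secondarily, the efficacy hypothesis points to unspecified traditional rates rather than the randomised standard arm

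*Protocol*

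**What the plan says.** In the Protocol, Background, Significance and Rationale, the argument opens with "Our justification for committing the non-responders to a second cycle of TMS is as following". Item 2 deals with patients randomised to standard TMS again. It cites a clinic series of 139 patients given 9 weeks of TMS, of whom 60 were responders at week 4 and 89 at week 8. It continues: "Of the 79 that did not respond at the 4 week measurement, 42 (more than 50%) responded at the week 8 point". The definition is given: "Response is defined here as a 50% or greater reduction in starting Ham D score". The conclusion drawn is that "even for the patients who receive the second round of standard TMS the above facts demonstrate the advantages of prolonged (4-8 week) treatment by TMS". The protocol then sizes that advantage with these words: "in the form of a 50% favorable outcome in that group of patients".

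Group 2 is described elsewhere. Inclusion criterion 12 for the second sample is "History of NON-response to rTMS in THIS depressive episode". The Overview of Study Design says "Group 2 (N=30) constitutes those who have previously demonstrated that they do not respond to standard TMS". These patients "will receive another cycle of standard versus targeted TMS", and the scan that precedes the second cycle is placed after the first cycle ends. Non-response is a fall of less than 50% in HDRS-24 from baseline.

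Specific Aims and Hypotheses contains one efficacy hypothesis: individualised targets will give response rates above those traditionally seen with rTMS. It gives no rate, source or population. The Overview of Study Design and the section on TMS treatments for Group 2 randomise these patients to targeted or standard TMS, and the Overview keeps raters and patients blinded.

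**The concern.** The 42/79 is the only response rate offered in support of randomising prior non-responders to standard TMS again. It was observed in patients part-way through a course who simply continued it. Group 2 patients are re-treated after a cycle that ended without response. Late response during a course and response to a new course after failure are different quantities, and the first does not estimate the second. An ethics board or referring clinician reading item 2 would take away an expectation of roughly one in two for the standard arm that the data do not support.

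The hypothesis has a related, smaller weakness. A traditional rTMS rate is not specific to patients who have already failed rTMS. Set against such a benchmark, the targeted arm could look poor because its patients are harder to treat, or look good because the benchmark was chosen loosely. The randomised standard arm avoids both problems, yet the hypothesis does not mention it.

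**Working it through.** **Inputs.** From Background, item 2: 139 treated; 60 in response at week 4; 89 in response at week 8; 42 of the week-4 non-responders in response at week 8. From the Overview of Study Design: targeted N=20, standard N=10.

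**1. Reproduce the plan's figure.**
- Not in response at week 4: 139 − 60 = 79.
- In response at week 8 among these: 42/79 = 53.2% (exact 95% CI 41.6% to 64.5%).

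The protocol's statement that this exceeds 50% is arithmetically right as an observed proportion.

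**2. Reconcile the counts.**
- If every week-4 responder had kept response, week 8 would show 60 + 42 = 102. The protocol gives 89.
- Implied week-4 responders no longer in response at week 8: 102 − 89 = 13.
- Not in response at either week 4 or week 8: 79 − 42 = 37.
- All not in response at week 8: 37 + 13 = 50, which equals 139 − 89. As a share, 50/139 = 36.0% (exact 95% CI 28.0% to 44.5%).

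**3. Compare the populations.**

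| | Behind the 50% | Group 2 |
|---|---|---|
| Status at the start of the interval | Not in response at week 4 of a 9-week treatment | Non-response to rTMS in this episode, first cycle finished |
| Treatment that follows | Continuation of the same treatment | A further cycle of 36 sessions over 9 weeks |
| Response observed | At week 8 of that treatment | No rate given in the protocol |

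The clinic definition of response (a reduction of 50% or more) and the study definition of non-response (a decrease of less than 50%) are complementary on the percentage scale. The clinic's Hamilton version is not stated; the study uses HDRS-24. On that reading the 42 are responders at week 8. **If** first-cycle non-response is judged at week 8 or later, none of the 42 would qualify for Group 2. The nearest clinic patients are then the 50 not in response at week 8, or the 37 if loss of an earlier response does not count as non-response. No re-treatment outcome is given for either set.

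**4. What the randomised contrast can show.** The protocol states no alpha, power or effect size for Group 2, so this step is illustration only. Assume 20 versus 10 patients, a two-sided Fisher test at 0.05 and 70% response on targeted TMS:

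| Assumed standard-arm response | Power |
|---|---|
| 20% | 66% |
| 30% | 45% |
| 53.2% | 12% |

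The randomised comparison is the better-matched reference, but it is imprecise at this size, and how imprecise depends on a standard-arm rate that the protocol does not supply.

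**The case against.** **Item 2 is open about its data.** It prints every count, both time points and the response definition, and it speaks of prolonged treatment, so an attentive reader can see what was measured. The group to which the 50% refers could be read as the week-4 non-responders. This is fair, and it makes the error easy to find. But the sentence is about patients in the second round of standard TMS, and the list exists to justify a second cycle. Item 2 also says the clinic statistics agree with published application guidelines. That source is not available here, and the text reports no re-treatment rate from it.

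**The length of the failed first cycle is not stated.** This stands. A reader might infer that none of the 42 could ever enter Group 2. The documents support that only if non-response is judged at week 8 or later. Had the first cycle ended near week 4, the figure would come closer to fitting, though nothing shown says that it did, and the timing table and diagram are attachments not seen.

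**Little depends on the figure.** This also stands. No sample size or power uses it. The protocol offers targeted treatment to standard-rTMS non-responders at the end of the study, has alternatives discussed before the second course, and states that there are no direct benefits, though it adds that targeting may improve response.

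**The hypothesis is a matter of wording.** The Lay Summary aims to show targeted TMS superior to conventional approaches, which is compatible with the randomised contrast, and a statistical analysis plan may fix the test. A reader might infer that no between-arm comparison is planned; the documents do not support that. What remains is that the one efficacy hypothesis the protocol does state uses a less suitable reference than the one its design provides.

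**Conclusion.** The point holds as a misapplied figure. The 53.2% (42/79) is response during continued treatment within one 9-week course, and it cannot serve as support for a second standard cycle in patients whose first cycle finished without response. The protocol contains no estimate of that quantity. The closest clinic patients, 50/139 (36.0%) not in response at week 8, comprise 37 in response at neither time point and, by implication of the counts, 13 who lost an earlier response.

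Three stronger readings should be resisted. The documents do not show that response to a second standard cycle is low, or that it is unknown in general; they show only that this protocol gives none. The mismatch between 60 + 42 and 89 is not a counting error, since loss of response explains it. Nor does the point show that re-treatment with standard TMS is unjustified; no view is taken on whether a second cycle is clinically appropriate.

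The hypothesis wording is a secondary matter. It names an unspecified benchmark not matched to prior non-responders, while a blinded randomised comparator is already in place. Both parts should be corrected; neither invalidates the design.

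**What to change.** **Background, item 2.** Describe the clinic data as response during continued treatment within one 9-week treatment. Withdraw the 50% as support for a second standard cycle. State that this protocol provides no estimate of response to a second standard cycle after non-response.

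**Specific Aims and Hypotheses.** By dated amendment, state the efficacy hypothesis as targeted versus concurrently randomised standard TMS within Group 2, keep any comparison with traditional rates descriptive, and acknowledge that about 20 versus 10 patients gives an imprecise estimate.

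Because enrolment is under way, the amendment should record enrolment at its date and whether any Group 2 outcomes by arm have been seen. The counts need reconciling first: Overall Progress gives 28 enrolled and 26 completed, while Sample Demographics lists 24 and 10 by population, which sum to 34. Patients counted in both groups might explain the difference, but the protocol does not say so.

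**Cost.** The first change is wording only. The second needs an amendment. Neither alters sample size, visits or procedures. The price is a less favourable rationale for the standard arm and an explicit admission of limited precision.
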